### 7.1.3 Dose Modification

#### 7.1.3.1 Non-hematologic:

There will be no non-hematologic dose modifications in this study.

#### 7.1.3.2 Hematologic:

There will be no hematologic dose modifications in this study.

#### 7.1.3.3 Other considerations:

Not applicable

### 7.1.4 Safety Considerations

Evolocumab is not predicted to induce any specific immunologic adverse events given its well described safety profile. Although there is potential for immune-genicity, it has been evaluated using an electro-chemi-luminescent bridging screening immunoassay for the detection of binding anti-drug antibodies.

For patients whose sera tested positive in the screening immunoassay, an *in vitro* biological assay was performed to detect neutralizing antibodies. In a pool of placebo- and active-controlled clinical trials, 0.3% (48 out of 17,992) of patients treated with at least one dose of evolocumab tested positive for the development of binding antibodies. Patients whose sera tested positive for binding antibodies were further evaluated for neutralizing antibodies; none of the patients tested positive for neutralizing antibodies. There was no evidence that the presence of anti-drug binding antibodies impacted the pharmacokinetic profile, clinical response, or safety of Evolocumab . Therefore, we do not anticipate any immunologic AEs that can affect the patients wellbeing or with standard of care treatment of radiation therapy and temozolomide (XRT/TMZ). If any reactions are observed, the study team will pause the study and re-evaluate.

### 7.1.5 Missed Doses

Not applicable.

### 7.1.6 Concomitant Medications

Concomitant medications will be managed by the treating physician and recorded at each study visit by the study team.

As we wish to monitor immune modulation in both treatment and control groups, corticosteroids should be used at the lowest dose possible [less than 0.1 mg/Kg/day (<4 mg of dexamethasone / day)], except for the 24 hours prior to surgery or biopsy, to control symptoms of edema and mass effect, and discontinued, if possible. Use of corticosteroids should be recorded in the electronic database.

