## 10 SCREENING AND ON-STUDY TESTS AND PROCEDURES

Table 4. Schedule of Events for Treatment Arm

Description	Screening (within 14 days of starting evolocumab)	Treatment Period	Active Follow-up Period

	Pre-Evolocumab Screening	Evolocumab Injection	Surgical Procedure	Post-Operative Visit
Day(s)		1	4-14	Typically ~2 weeks following surgery
General Evaluations				
Evolocumab Informed Consent	X 			
Physical Exam	X			X
Neurologic Exam	X			X
Adverse Events			Continuous 	
Laboratory Evaluations				
CBC with differential	X			X
CMP	X			X
Lipid profile	X			
Serum Pregnancy Test, if applicable	X 	X 		
Pharmacokinetic blood draws (5 mL) 		X	X*	
Tumor tissue analysis (estimated >20mg available) 			X	
Treatment				
Evolocumab		X		

\* This blood sample taken at time of surgery or biopsy so that drug level in the blood can be compared to intratumoral concentration.

**Table 4** shows the schedule of events for the treatment arm of this study, including all study-related general evaluations, laboratory evaluations, disease evaluations, and treatments. Of particular importance for this phase 1 study are the tumor sampling and pharmacokinetic blood draws to investigate evolocumab concentration profiles following agent administration. Patients who consent to participate as a control will only be asked to have the following:

- Informed consent on the control consent form
- PK blood draw prior to surgical procedure
- Tumor tissue analysis, if available

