## 10.1 Screening Examination

The initial screening examination will take place at a Duke PRTBTC clinic visit. The patient will sign either the main Evolocumab treatment consent form or the control consent form for this study and then undergo peripheral blood draw (prior to administration of evolocumab for those in the treatment arm). All patients with resectable tumors or tumors amenable to biopsy will complete screening and confirm their eligibility per the inclusion/exclusion criteria in Section 9. Screening tests in the treatment arm will consist of a physical and neurological exam, CBC with differential, CMP, lipid panel, and Beta HCG quantitative (if applicable).

 Consent can be obtained within 30 days before starting evolocumab.

 Patients in the treatment arm will be followed for ongoing serious adverse events and new onset serious adverse events for 30 days following evolocumab injection.

 Within 48 hours of the first evolocumab injection, if applicable. Will only be repeated on Day 1 if screening pregnancy test is outside of the 48-hour window.

 Tube type to be determined by the Proteomics Core.

 Estimated > 50-100 mg from surgical resection or de-bulking procedure; Estimated > 20 mg from a minimum of 2 cores from biopsy

Once the patient is confirmed eligible, patients in the treatment arm will then receive Evolocumab via subcutaneous injection 4-14 days prior to surgical procedure. If the first evolocumab injection does not start within two weeks of the screening visit, the CBC with differential, CMP, lipid panel, and clinic visit (physical/neuro exam) will need to be repeated.

Patients who consent to participate as a control will not undergo any screening tests or procedures.

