## 10.3 Treatment Period

### Day 1:

- Baseline pharmacokinetic (PK\_ blood draw (applies to patients who consent to either arm of the study) (5 mL drawn). For patients in the treatment arm, PK blood draw should occur before Evolocumab injection. For patients in the control arm, this blood draw can occur prior to the scheduled day of the surgical procedure or on the day of the surgical procedure. [Error! Bookmark not defined.](#)

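### The low-corticosteroid rule covers both groups but has no pre-operative window for controls and no place in the analysis, so steroid exposure may confound the MHC-I and immune comparisons

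*Combined protocol and SAP*

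**What the plan says.** Section 7.1.6 sets the rule and gives its reason: "As we wish to monitor immune modulation in both treatment and control groups, corticosteroids should be used at the lowest dose possible". It states a daily ceiling, lifts it "except for the 24 hours prior to surgery or biopsy", and asks for steroids to be stopped where possible. On data capture it says "Concomitant medications will be managed by the treating physician and recorded at each study visit by the study team" and "Use of corticosteroids should be recorded in the electronic database". Neither sentence is limited to one arm. Neither gives a look-back period or a dose measure.

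For controls, the text under Table 4 in Section 10 says "Patients who consent to participate as a control will only be asked to have the following", and lists consent, one blood draw before the procedure, and tumor tissue if available. Section 10.1 adds: "Patients who consent to participate as a control will not undergo any screening tests or procedures". On timing, Section 10.3 allows the draw as late as the day of surgery: "For patients in the control arm, this blood draw can occur prior to the scheduled day of the surgical procedure or on the day of" ... No minimum interval between consent and surgery is set.

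Sections 3.3 and 7.1 allow BTBR specimens to stand in if control accrual is difficult. Section 7.1 describes 2:1 matching but names no matching factors.

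Section 13.4.2 plans a Wilcoxon rank sum or two-sample t-test between cohorts. Section 13.5.1 carries the same approach to MHC-I, and Section 13.6 uses the same tests for the immune and TIL endpoints. Section 13.2 summarizes baseline characteristics by arm without naming steroid exposure.

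**The concern.** The protocol itself treats corticosteroids as a threat to its immune readouts. Its safeguard works through management and recording before surgery, and the two arms have very different amounts of protocol-defined time before surgery. The arms are also not randomized, so nothing else balances steroid use between them. If exposure differs and steroids move a marker, an unadjusted comparison attributes the shift to evolocumab, or hides a real effect behind it. A positive or null MHC-I or TIL finding from this trial could then not be separated from steroid imbalance, and the data needed to examine the question might not exist in a usable form.

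**Working it through.** **Where the rule can operate**

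| | Treated | Consented control | BTBR control |
|---|---|---|---|
| Contact before surgery | Screening, Day 1, then 4-14 days (7.1, Table 4) | Consent and one draw, before or on the day of surgery (10, 10.1, 10.3) | None under this protocol |
| Can the ceiling apply? | Yes, for days | Only if consent comes more than 24 hours ahead; not required | No |
| Steroid recording | 7.1.6, no window or dose measure | Same | Not stated |
| Steroid dose in eligibility (9.1, 9.2) | No | No | No |
| Use in 13.2, 13.5.1, 13.6 | None named | None named | None named |

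A control first seen on the day of surgery is already inside the exempt 24 hours, so the ceiling never applies to that patient while on study.

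**How much an imbalance could matter**

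The plan states no alpha, power, effect size or SD (Section 13.8 gives practical grounds for the sample size), so there is no planned figure to reproduce. What follows is an illustration.

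From the documents: 10 treated, 20 controls, unadjusted two-group test. Assumed: two-sided 0.05; a steroid effect of 1 SD on the marker; no drug effect; exposure proportions p_T and p_C.

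- Expected false difference = (p_C − p_T) × 1 SD. For 30% vs 70%: 0.40 SD.
- Exposure varies within each arm, so the within-arm SD is √(1 + p(1 − p)). For p = 0.3 or 0.7: √1.21 = 1.10.
- Noncentrality = difference / (SD × √(1/10 + 1/20)) = 0.40 / (1.10 × 0.387) = 0.94 on 28 df, which gives P(p<0.05) = 14.8%.

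Simulation of 200,000 trials per scenario, with exposure drawn patient by patient:

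| Treated vs control exposed | False difference | Formula | t-test | Wilcoxon |
|---|---|---|---|---|
| 50% vs 50% | 0 | 5.0% | 5.0% | 4.3% |
| 40% vs 60% | 0.2 SD | 7.3% | 7.4% | 6.6% |
| 30% vs 70% | 0.4 SD | 14.8% | 15.0% | 13.4% |
| 20% vs 80% | 0.6 SD | 28.4% | 28.9% | 26.3% |

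Treating the shift as fixed and leaving out the within-arm spread would overstate these as 7.9%, 16.9% and 32.2%. Reversing the imbalance (70% treated, 30% control) gives the same 15% with the opposite sign.

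**The case against.** A reader might infer that the rule can act only on treated patients and that controls have no visit at which medications could be noted. The documents do not support that. Section 10.1 has controls consent and give blood around a clinic visit, and that visit may precede surgery. The recording sentences in 7.1.6 apply to both arms. Section 10.9.1 takes current medications from the institution's electronic system without limiting this to treated patients, whereas 10.9.2 does limit the physical exam. A control who consents days ahead can be managed under the rule.

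A reader might also infer that controls will have more edema and more steroid, because treated patients must be able to wait 4-14 days, and so that the bias favors evolocumab. That is plausible but undocumented. Section 7.1 recruits controls under similar eligibility criteria, and inclusion criteria 1-3 are shared. Nothing in the documents shows that steroids lower MHC-I on tumor cells; 7.1.6 expresses only a general concern about immune modulation.

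Two further points are fair. The rule is soft in both arms: it is worded as advice, steroid dose is not an eligibility criterion for anyone, and Table 4 has no medication row even for treated patients. And the stakes are limited: Section 3.3 calls the control comparison exploratory, Section 13.8 describes it as descriptive, and BTBR use is a contingency.

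These points remove the absolutes and the claim about direction. They do not supply a window, a dose measure, BTBR steroid data or an analysis. A descriptive contrast is biased in the same way as a tested one, and Sections 13.5.1 and 13.6 still plan tests.

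**Conclusion.** The concern holds in a limited form. The steroid safeguard is not made operational for prospective controls, cannot reach BTBR controls, and feeds into no analysis, so a confounder that the protocol itself names would go unexamined in a non-randomized comparison. It bears on MHC-I and the immune/TIL endpoints. The documents give no basis for extending it to the drug level in tumor.

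The size is unknown. Under the assumed 1 SD effect, a 40-point imbalance would give about a 15% chance of a nominally significant result with no drug effect, and imbalances of 20 to 60 points about 7% to 29%. Those figures rest wholly on the assumed exposure rates and effect; the gap in the plan does not. It should be corrected, but it does not undermine the trial's main purpose.

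**What to change.** 1. In Sections 7.1.6 and 10.9.1, require chart abstraction of daily corticosteroid dose (dexamethasone equivalent) for the 14 days before tissue collection, including the last 24 hours, for every treated and consented-control subject, and for BTBR subjects where records allow. Fourteen days matches the longest injection-to-surgery interval.
2. In Section 13.2, report that exposure by arm, with the number of subjects for whom it is missing.
3. In Section 13.5.1 (MHC-I) and Section 13.6, pre-specify a sensitivity analysis adjusted for, or restricted by, that exposure, shown beside the main comparison. State that it will be imprecise. In the 30% vs 70% example, restriction to unexposed patients leaves 7 treated and 6 controls, with a standard error of √(1/7 + 1/6) = 0.56 SD.

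The cost is chart review at one institution for about 30 subjects (10 + 20) and one added table. It needs no new visit, sample or patient, and the clinical steroid rule is left as it is.

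Separately, the two expressions of the ceiling in 7.1.6 (0.1 mg/kg/day and 4 mg of dexamethasone a day) agree only at 4 / 0.1 = 40 kg, and at 70 kg the first gives 7 mg. They must be reconciled before any exposure category is defined from the ceiling.

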## 9 SUBJECT ELIGIBILITY

### 9.1 Inclusion Criteria

#### Both arms:

1. Adult patients  $\geq 18$  years old
2. Newly diagnosed or recurrent glioma or glioblastoma (GBM) (if recurrent, prior pathology report indicating glioma)
3. A clinical indication for gross macroscopic resection, debulking of the glioma, or biopsy, with sufficient tumor size that can allow collection of specimens for the required analyses.

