### **13.1 Analysis Sets**

All patients who receive Evolocumab will be included in summaries of adverse events.

PK and PD analyses will include all patients in the treated and untreated groups who have baseline PK blood collected and underwent a resection.

Analyses of serum and intratumoral levels of Evolocumab will be conducted among treated and untreated patients who were resected or biopsied and had serum collected.

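### Section 7.1.6 states one corticosteroid ceiling as two figures that, if both mean dexamethasone, agree only at 40 kg, so doses between them cannot be classed as within or above the limit

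*Combined protocol and SAP*

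**What the plan says.** Section 7.1.6 gives both the purpose and the scope of the limit: "As we wish to monitor immune modulation in both treatment and control groups, corticosteroids should be used at the lowest dose possible". The ceiling is "less than 0.1 mg/Kg/day (<4 mg of dexamethasone / day" in brackets, and it applies "except for the 24 hours prior to surgery or biopsy". The section also asks that steroids be stopped where that can be done, and adds: "Use of corticosteroids should be recorded in the electronic database".

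The section does not say which figure governs, whether the lower of the two applies, what reference weight links them, or whether the per-kilogram figure refers to dexamethasone or to another agent. Section 9 has no steroid or body-weight criterion.

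The analysis set in Section 13.1 does not depend on steroid dose: "PK and PD analyses will include all patients in the treated and untreated groups who have baseline PK blood collected and underwent a resection". Section 6 lists MHC-I expression as a secondary endpoint, and immune infiltration and TIL markers as exploratory ones. Sections 13.5.1 and 13.6 compare the arms by a Wilcoxon rank-sum or two-sample t-test and describe no covariate adjustment.

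**The concern.** A ceiling written as a per-kilogram dose with a fixed dose in brackets reads as one rule in two units. Here the two are far apart at usual adult weights, so two clinicians can both follow the text and work to different ceilings. Nor could an analyst later say whether a patient on a dose between the two was within the limit.

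The protocol itself ties the limit to immune monitoring in both arms, so what is at stake is how the immune comparisons are read. These set up to 10 treated patients against 20 non-randomized controls, and concomitant medication is managed by the treating physician. If steroid exposure differed between arms, the planned tests could not separate that from an effect of evolocumab, and no tabulation of exposure is planned that would reveal it.

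**Working it through.** **Inputs**
- Per-kilogram ceiling: below 0.1 mg/kg/day (Section 7.1.6).
- Absolute ceiling: "<4 mg of dexamethasone / day" (Section 7.1.6).
- Population: adults, with no weight criterion (Section 9.1).
- Assumption 1: both figures refer to dexamethasone, the only agent the section names.
- Assumption 2: body weight. The documents give none; 50 to 90 kg is taken as an illustrative range.

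**Step 1: can the bracketed 4 mg/day be reproduced from 0.1 mg/kg/day?** Daily ceiling (mg) = 0.1 × weight (kg). Setting this equal to 4 gives weight = 4 / 0.1 = 40 kg. The plan's figure is reproduced at that weight and at no other.

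**Step 2: size of the gap.**

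| Weight (kg) | 0.1 × weight (mg/day) | Ratio to 4 mg/day | 4 mg/day in mg/kg/day | Doses meeting the per-kg figure only (mg/day) |
|---|---|---|---|---|
| 40 | 4 | 1.00 | 0.100 | none |
| 50 | 5 | 1.25 | 0.080 | 4 to <5 |
| 70 | 7 | 1.75 | 0.057 | 4 to <7 |
| 90 | 9 | 2.25 | 0.044 | 4 to <9 |

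**Step 3: which doses are ambiguous.** For a patient above 40 kg:
- A dose under 4 mg/day meets both figures.
- A dose of 0.1 × weight or more breaks both.
- A dose from 4 mg/day to just under 0.1 × weight meets the per-kilogram figure and breaks the absolute one. Exactly 4 mg/day falls in this band.

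Below 40 kg the order reverses: at 35 kg the per-kilogram figure is 3.5 mg/day and is the stricter one.

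**Step 4: what in the plan uses the limit.** No eligibility criterion in Section 9, no steroid-specific withdrawal reason in Section 10.8.1 and no analysis-set rule in Section 13.1 refers to it. The primary endpoint, evolocumab in tumor by mass spectrometry, is not what the limit was written to protect. The link is to the immune readouts.

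**The case against.** The case for treating this as a small wording matter is a fair one.

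- **The band is limited.** A reader might infer that no ordinary adult's adherence can be determined. That is too strong: above 40 kg, any dose under 4 mg/day satisfies both figures, and the section asks for the lowest workable dose in any case. The documents do not say how many patients would fall in the band. This stands.
- **The 40 kg figure is conditional.** It needs both figures to mean dexamethasone. If the per-kilogram figure was meant for another corticosteroid, the crossover point changes, but the text would still be unclear because it does not say so.
- **The limit is advisory and has a gap.** It excludes nobody, and the 24 hours before tissue is taken are exempt. Reconciling the figures leaves that exposure uncapped. This stands, and it is a reason to record dose in that window.
- **Differential bias is not shown.** A reader might infer that the ambiguity biases the arm comparison. The same sentence covers both arms at one center, and nothing in the documents indicates that it would be read differently by arm. In a non-randomized comparison, steroid use could differ even under a single clear figure.
- **Absence of control screening is not evidence.** A reader might take "Patients who consent to participate as a control will not undergo any screening tests or procedures" (Section 10.1) to mean that the limit is applied unequally. It does not show that: the treatment-arm screening list has no steroid check either.
- **MHC-I specifically.** Section 7.1.6 speaks of immune modulation in general; the documents do not state that steroids alter MHC-I.

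The inconsistency itself survives these objections, because no other section settles it.

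**Conclusion.** The ceiling is internally inconsistent as written. If both figures mean dexamethasone, they agree only at 40 kg, and over an assumed 50 to 90 kg the per-kilogram figure is 25% to 125% above the absolute one. Only doses between the two figures are ambiguous.

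The consequence is confined to consistent steroid management, and to the reading of the MHC-I and TIL comparisons, where an imbalance between arms is possible but undemonstrated. The primary endpoint and the analysis sets are untouched. The documents support a correction that should be made, not a claim that the immune results will be biased. No view is taken on which figure is right.

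**What to change.** 1. **Reconcile Section 7.1.6.** The investigators should state the agent, say which figure governs, and apply the result to both arms.
2. **Record what is needed to use it.** The section asks only that use be recorded. Specify agent and dose, including in the exempt 24 hours. If a per-kilogram figure is kept, record body weight too, since none is scheduled for consented controls. For biorepository controls, whom a prospective limit cannot bind, take the same items from existing records where available.
3. **Add to Sections 13.5.1 and 13.6.** Tabulate steroid exposure by arm beside the MHC-I and TIL results. Repeat those comparisons, descriptively, without patients above the reconciled limit.

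The cost is one corrected line, a few extra data fields and one table. With at most 10 treated patients against 20 controls, the sensitivity comparison will be imprecise, so the by-arm table is the more useful of the two. Some biorepository records may be incomplete, and the table should show how many are.

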### 7.1.7 Study Drug Blinding

Not applicable.

## 7.2 Rationale for Selection of Dose, Regimen, and Treatment Duration

The primary objective of this study is to determine whether evolocumab can cross the blood brain barrier and accumulate intratumorally. This drug has been approved by the FDA, and the safety data are well understood .

Therefore, the maximum clinically indicated dose for hyperlipidemia (420 mg subcutaneously into thigh, abdomen or upper arm) will be used . Only a single dose is required 4-14 days prior to administration as this is the point at which peak plasma concentrations occur and maximal accumulation in the brain is likely to occur, but remaining well within the effective half-life of 11-17 days. This will therefore allow for the

greatest chance for detected evolocumab in the brain, should it successfully cross the blood brain barrier. No dose escalation is planned.

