### **3.3 Design and Procedure**

A maximum of 10 patients with pathologically documented glioma (either newly diagnosed or at first progression/ recurrence) will be treated with Evolocumab in this study after providing informed consent. Patients will receive 420 mg (the maximum single dose) of Evolocumab subcutaneously into thigh, abdomen or upper arm 4-14 days prior to a surgical procedure or biopsy of their tumor. After the procedure, leftover tissue not required for histological analysis will be collected, and the level of evolocumab will be quantified using liquid chromatography coupled to tandem mass spectrometry (LC-MS/MS). At two time points, prior to injection of Evolocumab and at time of surgery or biopsy, peripheral blood will be drawn to analyze serum levels of the drug (for comparison to intratumoral). Twenty to one hundred milligrams of tumor per patient will be homogenized and normalized using a protein assay followed by reduction/alkylation and trypsin digestion. Stable isotope-labelled (SIL) peptides corresponding to evolocumab-specific peptides will be spiked into tryptic digests, and LC-MS/MS will be used for targeted quantification of the drug-derived and SIL forms of these Evolocumab-specific peptides. Calibration curves will be generated by spiking in of Evolocumab into blank matrix (tumor homogenates from the brain specimen repository) followed by targeted LC-MS/MS. Data analysis, including normalization to SIL standards and fitting of data to the calibration curve will be performed in Skyline as previously described. If necessary, an immunoprecipitation step using Protein A/G agarose will be utilized to enrich for immunoglobulins (including evolocumab) prior to trypsin digestion and LC-MS/MS.

A contemporaneous control arm of 20 patients who undergo craniotomy (without receiving Evolocumab) will be consented to participate in this study as control subjects and prospectively observed. Although non-randomized, these specimens will provide valuable information for exploratory comparison of the evolocumab treated and evolocumab untreated tumor specimens and their immune microenvironment. If there are difficulties recruiting prospectively patients to serve as a control group, samples from the Brain Tumor Center Biorepository (BTBR) (Pro00007434) will be considered as possible control subjects.

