## 4 STUDY SCHEMA

\* Evolocumab may be given 4-14 days prior to surgical procedure.  
\* Safety monitoring will occur until routine post surgical procedure follow-up.

Figure 1. Study schema for newly diagnosed or recurrent glioma patients receiving Evolocumab

\* Peripheral blood draw on Day 1 can occur prior to day of surgical procedure or the day of surgical procedure.

Figure 2. Study schema for control patients

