## 5.2.2 Clinical Experience

Standard treatment for hypercholesterolemia relied on diet modification and use of statins until the introduction of antibodies, such as evolocumab, that inhibit proprotein convertase subtilisin-kexin type 9 (PCSK9). Evolocumab is an antibody that binds to PCSK9, where the antibody's therapeutic effect is to reduce LDL-cholesterol and where the therapeutic goal is to reduce risk for heart attack and stroke.

In phase II and III clinical trials (Open Label Study of Long Term Evaluation Against LDL- C [OSLER-1 and OSLER-2], respectively) evolocumab decreased LDL cholesterol by 52%, decreased total cholesterol by 36%, and raised high-density lipoprotein cholesterol by 7% when compared to standard treatment (Sabatine et al., 2015). A follow-up study (Further Cardiovascular Outcomes Research with PCSK9 Inhibition in Patients with Elevated Risk [FOURIER]) was performed to evaluate effects on reducing cardiovascular endpoints, such as myocardial infarction, stroke, unstable angina, or need for coronary revascularization. The combination of evolocumab plus standard statin therapy significantly reduced the risk of cardiovascular death, myocardial infarction, or stroke by 20%, which correlated with decreases in LDL levels. Evolocumab is currently FDA-approved for treatment of hypercholesterolemia in combination with other lipid-lowering medications (e.g., statins, ezetimibe), and is only recommended as

single- agent therapy in patients diagnosed with primary hyperlipidemia, which is typically an inherited disease. It is given as a 140-mg subcutaneous injection once every 2 weeks or 420 mg monthly .

Peak plasma concentrations occur at 3–7 days  and evolocumab has a half-life of 11–17 days and like other monoclonal antibodies, is eliminated by degradation to short peptides and amino acids. When considering adverse reactions, this has been well characterized as part of the FDA approval process. In a 52- week, double-blind, randomized, placebo-controlled trial, 599 patients received 420 mg of evolocumab subcutaneously once monthly. The mean age was 56 years (range: 22 to 75 years), 23% were older than 65 years, 52% women, 80% White, 8% Black, 6% Asian; 6% identified as Hispanic ethnicity. Adverse reactions reported in at least 3% of evolocumab-treated patients, and more frequently than in placebo-treated patients are shown in Table 1.

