## 10.4 Active Follow-up Period

### Days 4-14 – Surgical resection or biopsy

- Tumor tissue collection (applies to patients who consent to either arm of the study) – this tissue will be taken intraoperatively for pharmacokinetic LC-MS analysis to assess for the presence of evolocumab.
  - Sample will only be taken for analysis if greater than 20 mg of resected or biopsied tissue available (excess available beyond that required for histological analysis)
  - Sample to be aliquoted into 25 mg sections for resections and 10-20 mg (1-2 cores) for biopsies

Treatment arm only:

- Pharmacokinetic blood draw (5 mL, drawn at time of surgery or biopsy, i.e., PK draw may occur either immediately before or during surgery or biopsy)Error! Bookmark not defined.
- Adverse events monitoring

About 2 weeks following surgery or biopsy (treatment arm only)

- Physical and neurological exam
- Laboratory evaluations (obtained as part of standard post-operative labs)
  - CBC with differential
  - CMP
- Adverse events monitoring

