#### **13.5.2 Secondary Objective #3: Serum and Intratumoral Levels of Evolocumab**

Among patients treated with evolocumab, the third secondary objective is an assessment of the relationship between serum and intratumoral levels of the drug. These assessments will be obtained at the time of surgical procedure. A scatterplot will graphically show the relationship between these two measures. Spearman's rank correlation will assess their association.

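### The serum–tumour correlation in Section 13.5.2 ignores the time from injection to procedure, and the passages that justify and define the sampling window disagree.

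*Combined protocol and SAP*

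**What the plan says.** **Sampling and analysis.** Section 7.1 allows up to 10 treated patients. Section 13.5.2 pairs one serum with one intratumoral level per treated patient: "These assessments will be obtained at the time of surgical procedure". It plans a scatterplot, and "Spearman's rank correlation will assess their association". Neither that section nor Sections 3.6, 6, 13.1 or 13.4.2 adjusts for, stratifies by or displays the time since injection.

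**Justification of the window.** Section 7.2: "Only a single dose is required 4-14 days prior to administration as this is the point at which peak plasma concentrations occur". The sentence adds that brain accumulation is likely to be maximal then, and that the window lies within the half-life. Section 5.2.2: "Peak plasma concentrations occur at 3–7 days", and "evolocumab has a half-life of 11–17 days".

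**Definition of the window.** Section 3.3 has dosing "4-14 days prior to a surgical procedure or biopsy of their tumor". The Section 4 schema says "Evolocumab may be given 4-14 days prior to surgical procedure", and Sections 7.1 and 10.1 agree. Table 4 puts the injection on Day 1 and the procedure on Days 4-14. Section 10.4 uses the same label: "Days 4-14 – Surgical resection or biopsy".

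**The concern.** The third secondary objective asks how strongly serum and tumour levels are associated. Each treated patient gives one post-dose pair, and both members share that patient's interval. Serum declines after its peak. Tumour may follow serum closely or may still be filling. In the second case late sampling lowers serum and raises tumour, so patients' different intervals push the two measures apart. The pooled coefficient then partly measures scheduling. The amendment log says the current window was adopted for scheduling flexibility, so a real spread of intervals should be expected.

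The two textual conflicts matter in their own right. The peak statement in Section 7.2 is part of the pharmacokinetic case for the window. The day count decides whether a patient at the edge of the window is compliant.

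**Working it through.** The plan gives no power, alpha or effect size for this correlation, so there is no planned figure to reproduce.

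**1. Peak statements.** The window 4-14 contains 11 whole days. Days 4-7 (4 of 11) fall inside the 3-7 day peak of Section 5.2.2; days 8-14 (7 of 11) fall after it. Section 7.2 calls the whole window the peak. It also counts back from administration, where every other section counts back from the procedure.

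**2. Day count.** Injection on Day 1 and procedure on Day 4 is 4 − 1 = 3 days after injection; Day 14 is 14 − 1 = 13 days. Table 4 and Section 10.4 therefore allow 3-13 days after injection, and Sections 3.3, 4, 7.1 and 10.1 allow 4-14. A Day 4 procedure breaches the second rule. A procedure 14 days after injection falls on Day 15 and breaches the first.

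**3. Serum decline from the documents' half-life.** From day 7 to day 14 the fraction left is 0.5^(7/17) = 0.75 or 0.5^(7/11) = 0.64, a fall of 25% to 36%.

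**4. Effect on the coefficient (illustration).** From the documents: half-life 11 or 17 days, interval 4-14 days, n = 10. Assumed: intervals uniform, absorption half-life 1.5 days, tumour as a linked compartment, log-SD 0.3 for exposure and 0.3 for the tumour level.

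- Serum: S(t) ∝ F·[exp(−ke·t) − exp(−ka·t)], with ke = ln2/half-life and ka = ln2/1.5. The peak, ln(ka/ke)/(ka − ke), is 5.0 days (half-life 11) or 5.8 days (half-life 17), inside the 3-7 day range.
- Tumour: dC/dt = k·(S − C), with k = ln2/equilibration half-life.
- Benchmark at a fixed interval: log-scale correlation 0.3/√(0.3² + 0.3²) = 0.707. Large-sample Spearman = (6/π)·asin(0.707/2) = 0.69. Expected value at n = 10 = 6/(11π)·[asin(0.707) + 8·asin(0.354)] = 0.64.

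Large-sample pooled Spearman, against 0.69 at a fixed interval:

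| Equilibration half-life | Serum half-life 11 d | Serum half-life 17 d | No patient-level link (11 d / 17 d) |
|---|---|---|---|
| 3 d | 0.47 | 0.52 | −0.13 / −0.09 |
| 7 d | 0.29 | 0.39 | −0.25 / −0.15 |
| 14 d | 0.21 | 0.34 | −0.29 / −0.17 |

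At n = 10 in the same scenarios, the mean crude coefficient is 0.19-0.48 and the mean partial Spearman given the interval is 0.58-0.61, against 0.64. Drawing intervals continuously instead of in whole days gives 0.24-0.51 and 0.57-0.62.

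**5. Where the effect shrinks or changes direction.**

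- Equilibration half-life 0.25-1 day: large-sample crude 0.68-0.72 against 0.69, and 0.02-0.16 with no link. At n = 10 with fast uptake, crude is 0.64-0.66 and partial 0.63-0.64.
- Both log-SDs 0.7, equilibration 3-14 days: 0.59-0.66 against 0.69. Exposure 0.7 and tumour 0.3: 0.75-0.86 against 0.91.

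A second model draws peak time (3-7 days) and half-life (11-17 days) per patient, with 10% assay noise and no variation in the tumour:serum ratio. Mean coefficients at n = 10, shown as pooled / partial / fixed at day 7:

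| Exposure log-SD | Equilibration 0.5 d | 2 d | 5 d | 10 d |
|---|---|---|---|---|
| 0 | 0.52 / 0.26 / 0.12 | −0.03 / 0.22 / 0.18 | −0.42 / 0.12 / 0.19 | −0.50 / 0.11 / 0.16 |
| 0.2 | 0.77 / 0.74 / 0.74 | 0.52 / 0.68 / 0.72 | 0.20 / 0.62 / 0.70 | 0.08 / 0.61 / 0.70 |
| 0.4 | 0.89 / 0.89 / 0.89 | 0.78 / 0.86 / 0.87 | 0.60 / 0.82 / 0.87 | 0.51 / 0.80 / 0.87 |
| 0.7 | 0.95 / 0.95 / 0.95 | 0.90 / 0.93 / 0.94 | 0.80 / 0.90 / 0.94 | 0.74 / 0.89 / 0.94 |

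A clearly negative mean appears only in the first row with slow equilibration. At log-SD 0.2, a sample value at or below zero occurs in 26% (5 d) and 41% (10 d) of trials; at 0.4, in 3%-4%.

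**6. Precision.** For a coefficient of 0.5, the Fisher-z standard error is √((1 + 0.5²/2)/7) = 0.401, giving a 95% interval of −0.23 to 0.87. With one covariate the divisor becomes 6, the standard error 0.433, and the interval −0.29 to 0.88.

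**The case against.** The strongest reply is that the objective is descriptive. Section 6 asks only for the strength of the association, Section 13.8 sizes the study on practical grounds, and ten patients give a very wide interval with or without adjustment. A partial Spearman is also a different estimand, because it removes exposure differences that arise from timing. This stands as a reason to keep the crude coefficient and report the partial one beside it. It is no reason to leave the interval out.

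Second, the documents give neither the tumour uptake rate nor the between-patient variability. A reader might infer that pooling biases the coefficient downward or inverts it. The documents do not support that as a general statement: fast uptake leaves the coefficient unchanged or slightly raised, and larger variation between patients reduces the loss.

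Third, Section 7.2 does not rest on the plasma peak alone. It also invokes brain accumulation and half-life, and cites a source that Section 5.2.2 does not cite for its peak figure. So it cannot be said from the documents which peak statement is right, only that they conflict. Nor does the wording in Section 7.2 cause the statistical problem. The spread of intervals does, and correcting that sentence would leave the coefficient as it is.

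Fourth, a reader might extend the point to the primary objective and take a low tumour level in an early-sampled patient as failure to enter the tumour. Section 13.4.2 compares treated with untreated cohorts and has no such patient-level rule, and no effect on that comparison has been shown.

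**Conclusion.** The point holds in a conditional form. The unadjusted coefficient mixes timing with patient-level association, and the plan has no step that would reveal it. With 30% log-SDs and tumour equilibration over 3-14 days, both assumed, an expected 0.64 at n = 10 is reported on average as about 0.2-0.5. A partial Spearman recovers most of the loss. With uptake of a day or less the bias is nil or slightly upward, and with 70% log-SDs the loss is smaller. Reversal of the expected value needs slow uptake together with little or no patient-level variation or link.

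The two textual conflicts, on peak timing and on the day count, need no assumptions. The change is worth making because it is cheap and helps where timing matters. It does not call the primary analysis into question.

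**What to change.** 1. **Section 13.5.2.** Report a partial Spearman correlation given days from injection to tissue collection alongside the crude Spearman. Give both with confidence intervals and label both descriptive. Mark the interval on the planned scatterplot, and plot the tumour:serum ratio against it. State that the injection and tissue-collection dates are captured for every treated patient; the plan implies this without saying so.
2. **Sections 7.2 and 5.2.2.** Reconcile the two statements of when plasma levels peak, and correct the reference point in Section 7.2 (administration or procedure). No view is taken here on which peak statement is right.
3. **Sections 3.3, 4, 7.1 and 10.1 against Table 4 and Section 10.4.** Reconcile to one day count, chosen by the sponsor and used throughout.

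**Cost.** No new patients, samples or visits. The partial coefficient uses one degree of freedom, so its interval is slightly wider (at 0.5: −0.29 to 0.88 instead of −0.23 to 0.87), with little gain if timing turns out not to matter. Items 2 and 3 are wording changes once the sponsor has decided.
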